Dear Dr.,

This enclosed our Study Protocol with Statistical analysis plan (SAP).

Official title: Comparative study between nebuliezed and intravenous magnesium sulfate for treatment of persistant pulmonary hypertension in neonates

NCT number: NCT06603766

Document updated date: 4/2/2025

Study Protocol with SAP

After obtaining approval from the medical ethical committee of Benha University Hospital.

This study was conducted in Benha University Hospitals at Neonatal Intensive Care Unit (NICU) on neonates who were admitted for PPHN after delivery. An informed consent was obtained from parents after explaining the procedure.

Community design and sampling:

A non-randomized controlled trial on neonates who met inclusion criteria. It was carried on 40 mechanically ventilated neonates with severe PPHN who was divided into two groups:

- (A) Nebulized magnasium (NebMag) group (n= 20): received nebulized isotonic magnesium (64 mg/mL) and intravenous placebo.
- (B) Intravenous magnesium (IVMag) group (n= 20): received intravenous magnesium and nebulized placebo.

The study time frame was 24h.

Duration of the study:

The study was conducted for two years from October 2021 to septmber 2023.

Ethical consideration:

- The whole study design was approved by the local ethics committee, Faculty of Medicine, Benha University (Approval Number: 39-9-204).
- Confidentiality and personal privacy were respected in all levels of the study.
- Guardians felt free to withdraw from the study at any time without any consequences.
- Collected data was not and will not be used for any other purpose.

Inclusion criteria:

- 1) Newborns with documented PPHN as confirmed by ECHO.
- 2) Neonates born at \geq 35 weeks' gestation with a birth weight of 2.5–4 kg
- Neonates have to be connected to mechanical ventilation with an oxygenation index (OI) > 30 on two occasions at least 15 minutes apart.
- 4) The ECHO had to show a predominant right-to-left or bidirectional shunt (through ductus arteriosus and/or foramen ovale) and/or tricuspid regurgitant jet with a pressure gradient ≥ 2/3 of the systemic systolic blood pressure.

Exclusion criteria:

- 1) Infants of mothers who received magnesium sulfate within 48h before labor.
- 2) Congenital heart diseases other than PDA and patent foramen ovale.
- Major congenital anomalies, including congenital diaphragmatic hernia and lung hypoplasia.
- 4) Prior need for cardiopulmonary resuscitation.
- 5) Mean arterial blood pressure (MABP) < 35 mmHg despite therapy with volume infusions and vasoactive inotropes.
- **6)** Impaired kidney function; and prior administration of pulmonary vasodilators or prior administration of surfactant.

Methods of the study:

Patients included in the study were subjected to the following:

Complete history taking: Full antenatal and postnatal histories.

were obtained from all cases including:

- Demographic data (gestional age, sex, mode of delivery, birth weight).
- Associated condition (asphyxia, infection, polycythemia).

Clinical examination:

Full clinical examination: including general examination included vital signs, anthropmetric measurements, APGAR score in the 1st and 5th minutes (7).

systematic examination including chest and abdominal examination with emphasize on the cardiac examination including the apex site, 1st, and 2nd heart sounds and manifestations of heart failure (tachycardia, tachypnea and enlarged liver), musculoskeletal and central nervous system examination.

Radiological investigation

- Chest X-ray
- ECG: The ECG may provide suggestive or supportive evidence of pulmonary hypertension by demonstrating RV hypertrophy and strain, and right atrial dilatation
- ECHO: measures pulmonary artery pressure, low ventricular output and low ejection fraction and fraction shortening.

Laboratory analysis

- Pulse oximeter monitoring in the four limbs:
- Blood pressure monitoring in the four limbs.
- Serial arterial blood gases: Post ductal arterial blood samples were drawn before (baseline) and 6, 12, and 24 h following study drug administration for gas analysis PH, PaO2, PaCO2, HCO3).
- Ventilatory parameters were recorded from ventilator (PIP, PEEP, MAP, fiO2, rate/min).
- serum magnesium level was measured before and 12 h following study drug administration.

The protocol of administration of magnesium sulfate:

- For intravenous administration a magnesium sulfate 10% solution was prepared by diluting an intravenous form of magnesium sulfate heptahydrate 50% with glucose 5%. Pharmacy designed 60mL aliquots of magnesium sulfate 10% and similar aliquots of glucose 5% as a placebo was prepared. Study participants received either active drug or placebo through an intravenous line a loading dose of 2 mL/kg over 30 min (equivalent to magnesium sulfate 200 mg/kg in case of the active drug), followed by a continuous infusion at a rate of 0.5 mL/kg/h (equivalent to magnesium sulfate 50 mg/kg/h in case of the active drug) for the 24 h study duration.
- For nebulization, an isotonic solution of magnesium sulfate (64 mg/mL) was prepared by diluting an intravenous form of magnesium sulfate heptahydrate 10% with distilled sterile water, 4-ml aliquots of isotonic magnesium sulfate (256 mg) and similar aliquots of isotonic saline as a placebo was designed. a 4-mL aliquot of active drug or placebo was loaded every 15 min to the jet nebulizer of ventilator.

The primary outcome in this study has been the change in oxygenation index (OI) from baseline to 12 and 24 h following study drug administration. OI: monitoring the oxygenation trend helps to guide when a baby might need to be referred for ECMO. It is a useful guide to monitor regularly in babies with PPHN.

OI: Mean Airway Pressure x FiO2 x 100 ÷PaO2 (in Pka) x 7.5

OI was preferred as it considers both oxygenation status and ventilatory support, over merely reporting individual values of SpO2, PaO2, FiO2, and ventilatory parameters. Note: When you are calculating OI, be aware of which units of measurement you use for the PaO2 – kPa or mmHg (kPa x 7.5 converts to the equivalent PaO2 in mmHg). FiO2 is the inspired fraction (e.g. 21% = 0.21, 100% = 1.0)

The secondary outcomes have been the changes in (a) mean arterial pressure and VIS from baseline to 6, 12, and 24 h following study drug administration and (b) serum magnesium level from baseline to 12 h after study drug administration.

Statistical analysis

The data were coded, entered and processed on computer using SPSS (version 24). The results were represented in tabular and diagrammatic forms then interpreted. Mean, standard deviation, range, frequency, and percentage were use as descriptive statistics. The following tests were done: Chi-Square test X² was used to test the association variables for categorical data. Student's t-test was used to assess the statistical significance of the difference between two population means in a study involving independent samples, with normal distribution. The accepted level of significance was 0.05. P value >0.05 is non-significant, P<0.05 is significant (*)

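### Postnatal age at first study dose has no stated entry window, is not a named baseline variable and is not adjusted for, so an imbalance between the non-randomised groups could bias the 12 h and 24 h OI comparison

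*Combined protocol and SAP*

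**What the plan says.** Under Community design and sampling, the study is "A non-randomized controlled trial on neonates who met inclusion criteria". On allocation it says only this: "It was carried on 40 mechanically ventilated neonates with severe PPHN who was divided into two groups". No rule for assigning an infant to a group is given.

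The entry criteria that touch on age are "Newborns with documented PPHN as confirmed by ECHO" and a minimum gestation of 35 "weeks' gestation with a birth weight of 2.5–4 kg". The setting adds "on neonates who were admitted for PPHN after delivery". None of these states an age in hours or days at enrolment or at first dose.

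Under Methods of the study, the history is introduced as "Complete history taking: Full antenatal and postnatal histories", followed by an open list. Its demographic line reads "Demographic data (gestional age, sex, mode of delivery, birth weight". Age at first dose appears nowhere in the document.

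The primary outcome is the change in OI from baseline to 12 and 24 h after study drug. The Statistical analysis section lists descriptive statistics, chi-square and Student's t-test for independent samples, with significance at 0.05. It names no covariate, matching or propensity method. It does not say which test serves the primary outcome, but the t-test is the only one listed for comparing means.

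**The concern.** The outcome clock starts at first dose, and nothing ties first dose to time since birth. PPHN is a disorder of the period after birth, so it is clinically plausible, though not stated in the documents, that the next 24 h go differently for an infant treated within hours of birth and for one treated later. In a randomised trial, chance would tend to balance this factor. Here nothing in the design does. The placebo in each arm may help to mask route, but it does not balance who was put into which group.

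If the groups differed in age at first dose, the planned comparison would attribute the resulting difference in course to route. None of the four named demographic items stands in for age at treatment, since all are fixed at birth.

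**Working it through.** **What can be reproduced.** The only design figure is 40 infants, 20 per group. It comes without power, effect size or SD, so it cannot be reproduced. For scale, at two-sided 5% (sidedness is not stated, so two-sided is assumed) the difference detectable with 80% power is (1.960 + 0.842) × √(2/20) = 0.89 SD by the normal approximation, or 0.91 SD with the t distribution.

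**What the text contains.** Reading the whole document for an age limit, an age variable or an adjustment:

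- Entry window: Inclusion criteria and Exclusion criteria give none in hours or days.
- Named baseline variable: the history and examination lists do not include age at first dose.
- Adjustment: the Statistical analysis section plans none, for age or for anything else.

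**Illustration of the possible bias.** The documents supply n = 20 per group and α = 0.05. Two inputs are assumptions:

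- ρ, the within-group correlation of age at first dose with OI change, taken as 0.1 to 0.5
- d, the difference between groups in mean age, in SD units, taken as 0.25 to 1.0

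With a linear relation and no true route effect:

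- bias in mean OI change, in SD units: b = ρ × d
- noncentrality of the t-test: b × √(n/2) = b × √10 = b × 3.162
- false-positive rate: the two-sided rejection probability of a noncentral t on 38 degrees of freedom

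For ρ = 0.5 and d = 0.5, b = 0.25, the noncentrality is 0.25 × 3.162 = 0.79, and the rejection probability is 12.0%.

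| ρ | d = 0.25 | d = 0.5 | d = 1.0 |
|---|---|---|---|
| 0.1 | b = 0.025; 5.1% | b = 0.05; 5.3% | b = 0.10; 6.1% |
| 0.3 | b = 0.075; 5.6% | b = 0.15; 7.5% | b = 0.30; 15.2% |
| 0.5 | b = 0.125; 6.7% | b = 0.25; 12.0% | b = 0.50; 33.8% |

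**Would a baseline p-value reveal the imbalance?** For d = 0.5 the expected z is 0.5 × 3.162 = 1.58. The power is about Φ(1.58 − 1.96) = Φ(−0.38) = 35%. A non-significant baseline test at this sample size would therefore not show balance.

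**The case against.** Four arguments on the other side carry weight.

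**The data may exist.** A reader might infer that age at first dose cannot be checked or adjusted for. The documents do not support that. The demographic line sits under a full antenatal and postnatal history with an open list, so the text shows that age is not named, not that it was not collected. Apgar scores at 1 and 5 minutes and gases timed from study drug suggest that birth and first-dose times were known. This objection stands: the point is what was not specified or planned.

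**Entry is not wholly open.** The words newborns and neonates set a loose limit, and excluding infants already given pulmonary vasodilators or surfactant may narrow the age range further. That stands too, but none of it is a window in hours.

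**The bias is hypothetical.** Both ρ and d are assumed, nothing in the documents shows that the groups differed in age, and at the low end of the range the effect is negligible. A reader might take the upper figure as evidence that this trial is biased; it is not. A reader might also call age at first dose a time-dependent confounder, but it is fixed for each infant at the start of treatment and is an ordinary baseline factor.

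**Age is one factor among many.** The plan adjusts for nothing, not even baseline OI, so the deeper weakness is an unadjusted comparison of non-randomised groups. That is right, and adding age alone would not cure it. It argues for a fix that includes baseline OI, not for leaving age out.

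**Conclusion.** The point holds in a limited form. Age at first dose has no stated window, is not a named baseline variable and is not adjusted for. In groups formed without randomisation, an imbalance in it could be mistaken for a route effect on OI change at 12 h and 24 h.

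Whether this happened, and by how much, cannot be told from the documents. Under the assumed ranges the false-positive rate lies between about 5% and 34%; the middle cases (ρ of 0.3 to 0.5 with d = 0.5) give 7.5% to 12.0%. The result rests on the clinical assumption that age affects the 24 h course, on a linear relation, and on the chosen ρ and d. It is an inexpensive improvement worth making, not a demonstrated error in the trial's result.

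**What to change.** The study ran from October 2021 to September 2023, so everything below belongs in the report and should be labelled post hoc.

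1. Derive postnatal age in hours at first study dose from the birth and first-dose times. That both are in the charts is an assumption; if they are missing for some infants, say for how many.
2. Show age at first dose by group, with the size of the difference (in hours and in SD units) and not only a p-value.
3. Add an ANCOVA of OI at 12 h, and another at 24 h, on group, baseline OI and age at first dose. Report it beside the unadjusted comparison so that readers can see whether the estimate moves.

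The cost is chart abstraction for 40 infants and two covariates. Residual degrees of freedom fall from 38 (40 − 2) to 36 (40 − 4). The plan currently has no regression model, so one must be specified. Confounding by factors that were not measured, or that are left out of the model, would remain.

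### In a non-randomised comparison of routes, no lung-disease variable is named and the OI comparison is unadjusted, so a lung-disease imbalance could pass for a route effect

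*Combined protocol and SAP*

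**What the plan says.** All references are to the combined protocol and SAP.

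- **Allocation.** Community design and sampling describes "A non-randomized controlled trial on neonates who met inclusion criteria", and then: "It was carried on 40 mechanically ventilated neonates with severe PPHN who was divided into two groups". The groups are 20 and 20. No method of allocation is given.
- **Baseline history.** Under Methods of the study, the history is introduced by "Complete history taking: Full antenatal and postnatal histories". The items that follow are demographic data and "Associated condition (asphyxia, infection, polycythemia"). They are introduced as examples, so the list is not closed. PPHN is not classified by cause.
- **Other lung information.** Clinical examination provides for "systematic examination including chest and abdominal examination with emphasize on the cardiac examination". Radiological investigation lists a chest X-ray but says neither when it is taken nor what is read from it; the ECG and ECHO entries beside it do say what they show. Laboratory analysis states: "Ventilatory parameters were recorded from ventilator (PIP, PEEP, MAP, fiO2, rate/min").
- **Exclusions.** The Exclusion criteria remove "Major congenital anomalies, including congenital diaphragmatic hernia and lung hypoplasia" and also "prior administration of pulmonary vasodilators or prior administration of surfactant".
- **Outcome and analysis.** The primary outcome is the change in OI at 12 h and 24 h relative to baseline. OI is mean airway pressure times FiO2 times 100, divided by PaO2. Statistical analysis names chi-square for categorical data and Student's t-test for two independent means, at a significance level of 0.05. It names no covariate and no adjusted model.

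**The concern.** Randomisation would put any lung-disease imbalance down to chance, and the 5% error rate would already allow for it. Here the arms were formed some other way, undescribed, and could differ systematically in how many infants have aspiration, pneumonia or other airspace disease rather than clear lungs. The named items do not capture this. Infection does not separate pneumonia from sepsis, and ventilator settings and baseline OI describe severity rather than cause.

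Lung disease can act on each input to OI. If its course over 24 h differs from that of clear-lung PPHN, an arm with more affected infants will show a different mean OI change even when the two routes work equally well. The planned t-test would attribute that difference to the route. It could favour either arm or hide a real difference. A reader of results produced exactly as planned would see neither the imbalance nor its effect.

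**Working it through.** The plan has no sample-size calculation, SD or expected effect, so there is no figure to reproduce. What follows is an illustration.

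**Inputs from the documents:** 20 infants per arm; significance level 0.05 (sidedness not stated, taken as two-sided); unadjusted two-sample t-test.

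**Assumptions:** the routes are truly equal. Within each lung-disease stratum, OI change is normal with SD 1. Lung disease shifts OI change by g = 0.5, 1 or 1.5 SD. Overall prevalence is near 50%. The realised gap between arms is 5 infants (12 v 7 or 13 v 8) or 7 infants (13 v 6 or 14 v 7).

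**Step 1, bias.** Bias = (gap / 20) × g.
- Gap 5: 5/20 = 0.25, so the bias is 0.125, 0.25 or 0.375 SD.
- Gap 7: 7/20 = 0.35, so the bias is 0.175, 0.35 or 0.525 SD.

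For scale, at 20 per arm the t-test has 80% power for (1.960 + 0.842) × √(2/20) = 0.89 SD.

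**Step 2, false-positive rate with the counts held fixed.** The true standard error of the arm difference is √(2/20) = 0.316. The t-test estimates a larger one, because the mixture of strata widens the spread within each arm. For 12 v 7 and g = 1:
- Added sum of squares: 12×8/20 + 7×13/20 = 4.80 + 4.55 = 9.35.
- Pooled SD: √(1 + 9.35/38) = 1.116, so the estimated standard error is 1.116 × 0.316 = 0.353.
- Critical difference (t on 38 df = 2.024): 2.024 × 0.353 = 0.714.
- Upper tail: (0.714 − 0.25)/0.316 = 1.47, probability 0.071. The lower tail adds 0.001.

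This gives about 7%. It ignores sampling variation in the estimated SD. Simulation, with at least 300,000 trials for each split, includes that variation and gives 8.1%.

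| Shift in OI change | Gap of 5 | Gap of 7 |
|---|---|---|
| 0.5 SD | about 6% | 7.6% |
| 1 SD | 8.1% | about 14% |
| 1.5 SD | about 10% | about 21% |

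**Step 3, would a baseline test reveal it?** At 20 per arm, a test of two proportions has about 25% power to detect 30% v 50%, and about 48% for 30% v 60%. A non-significant chi-square would not show balance.

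**Step 4, cost of adjusting.** If the covariate is unrelated to OI change, the standard error is multiplied by 1/√(1 − r²), where r is the correlation between arm and covariate. Near 50% prevalence, r is about 0.25 for a gap of 5: 1/√(1 − 0.0625) = 1.033, or about 3%. For a gap of 7: 1/√(1 − 0.1225) = 1.068, or about 7%.

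**The case against.** **The information probably exists.** A reader might infer that lung disease was never recorded and can be neither checked nor adjusted for. The documents do not support that. Histories, chest examination and chest X-rays were part of the work-up, the list of history items is open, and infection may capture pneumonia in part. What stands is narrower: the plan names no such variable, no balance check and no adjustment.

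**The route argument goes beyond the text.** A reader might add that aerosol reaches only ventilated lung, so lung disease also governs how well the nebulized drug works. That is plausible, but the documents do not say it. It also describes effect modification, which a main-effect covariate neither tests nor corrects. The confounding point does not need it. Nor do the exclusions prove that the plan treats lung state as prognostic: hernia and hypoplasia are excluded as major anomalies, and surfactant is paired with prior vasodilators, with no reason given.

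**Larger figures are available but do not fit the scenario.** Treating the gap as a difference in underlying prevalence gives about 11% and 16% at 1 SD. For a realised gap of 5 or 7 infants the rates are the lower ones above. It is also true that a gap of 5 or more would arise about 15% of the time by chance allocation at 50% prevalence, but the nominal 5% already covers such gaps. That figure says nothing about this allocation.

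**The endpoint is change, and all infants entered with OI above 30 on two occasions.** This removes part of any difference in level. It does not remove a difference in 24-hour course, though the documents offer no evidence on how large that difference is.

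**The plan adjusts for nothing at all.** This is correct: one covariate does not cure a non-randomised comparison. It is a reason to include baseline OI as well and to limit what is claimed for the adjustment.

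**Conclusion.** The point holds as a gap in the plan: arms not formed by randomisation, no named lung-disease variable, and an unadjusted comparison of an outcome whose inputs lung disease can affect. Under the stated assumptions, a realised gap of 5 to 7 infants raises the false-positive rate from 5% to about 8% to 14% at a 1 SD shift, with extremes of about 6% (0.5 SD, gap 5) and 21% (1.5 SD, gap 7). Shift, prevalence and gap are all assumed, and the documents do not show that an imbalance occurred. The conclusion does not extend to saying that lung disease cannot be recovered from the records, or that the route effect depends on it. The change is worth making because it is cheap and bears on the primary comparison.

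**What to change.** The study period ended in September 2023, so the remedy lies in existing records and in reporting.

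1. Code one binary variable, parenchymal lung disease (yes/no), from the chest X-rays and histories already obtained. Use only records that predate the first dose, and have the coder work without reference to arm or outcome. The plan does not state the timing of the X-ray, so this must be checked for each infant.
2. Tabulate the variable by arm as counts, and do not rely on a significance test to show balance.
3. Report the 12 h and 24 h between-arm OI comparisons adjusted for this variable and for baseline OI, which the primary outcome already requires. With 40 infants, few further covariates can be supported.
4. If pre-dose records cannot supply the variable, state that the OI difference is not adjusted for lung disease and may partly reflect it.

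**Cost:** some retrospective coding, with no new procedure or patients. If the covariate is unrelated to OI change, the standard error is about 3% larger at a 5-infant gap. The adjustment does not remove other confounding, and it does not test whether the route effect differs by lung disease.

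### Change in oxygenation index at 12 h and at 24 h are both primary, with no success rule or multiplicity control; if either counts, the false-positive rate is above 5% and can reach 9.75%

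*Combined protocol and SAP*

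**What the plan says.** The combined protocol and SAP states the primary outcome just before the Statistical analysis section: "The primary outcome in this study has been the change in oxygenation index (OI) from baseline to 12 and 24 h". The two times have equal standing.

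The Statistical analysis section is a single paragraph. For comparing means between groups it names one method: "t-test was used to assess the statistical significance of the difference between two population means in a study involving independent samples", for normally distributed data. Its only decision rule applies to P values one at a time: "The accepted level of significance was 0.05. P value >0.05 is non-significant, P<0.05 is significant".

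The document nowhere ranks 12 h against 24 h, divides alpha, adjusts for two tests, or specifies a repeated-measures or other joint test. It does not say what pattern of results makes the trial positive.

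Two other statements bear on the remedy:

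- **Allocation** (Community design and sampling): "A non-randomized controlled trial on neonates who met inclusion criteria", with 20 infants per group.
- **Timing**: the Duration of the study section says "The study was conducted for two years from October 2021 to septmber 2023", and the cover text says "Document updated date: 4/2/2025".

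**The concern.** Comparing two groups at two primary times with the listed test gives two primary P values. With no rule to combine them, two readings are open:

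- **Either time suffices.** The trial has two chances at its primary claim, each at 0.05.
- **Both times must succeed.** The error rate is held below 5%, but a result at one time only is a failure.

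The plan does not choose. If 12 h and 24 h disagree, it does not say what the trial concludes, and the favourable time could be presented as the primary result. With 20 infants per group and no sample-size calculation, disagreement is a realistic prospect.

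**Working it through.** **Inputs from the document.** Two primary times; significance level 0.05, unadjusted; independent-samples t-test; 20 versus 20. The document gives no overall error rate, so there is no figure of the plan's own to reproduce.

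**Assumptions.** Two-sided tests (sidedness is not stated), normally distributed change scores, comparable groups with no treatment effect, and a correlation ρ between the 12 h and 24 h changes. No value of ρ is given, so a range is used. One reference point: both changes subtract the same baseline. If the index has equal variance σ² at all three times and equal correlation r between any two, then

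- Cov(X12 − X0, X24 − X0) = rσ² − rσ² − rσ² + σ² = σ²(1 − r)
- Var(change) = 2σ²(1 − r)
- ρ = σ²(1 − r) ÷ 2σ²(1 − r) = 0.5

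Values of 0.5 to 0.9 are therefore more plausible here than 0.

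**Step 1: independence.** P(at least one significant) = 1 − 0.95² = 1 − 0.9025 = 9.75%.

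**Step 2: correlated tests.** With Z12 and Z24 bivariate normal:

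- Either: 1 − P(|Z12| < 1.96 and |Z24| < 1.96)
- Both: 5% + 5% − either
- Share of either-time false positives that are significant at one time only: (either − both) ÷ either

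| ρ | Either significant | Both significant | One time only, share |
|---|---|---|---|
| 0 | 9.75% | 0.25% | 97% |
| 0.5 | 9.07% | 0.93% | 90% |
| 0.7 | 8.35% | 1.65% | 80% |
| 0.8 | 7.81% | 2.19% | 72% |
| 0.9 | 7.04% | 2.96% | 58% |
| 0.99 | 5.66% | 4.34% | 23% |

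The either-time rate exceeds 5% for any correlation below 1. False positives confined to one time are the majority up to ρ = 0.9, but not at 0.99.

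**Step 3: t-tests at the actual group size.** Simulating two t-tests per trial with 20 per group (400,000 trials per value of ρ) gave either-time rates of 9.8%, 9.1%, 8.4%, 7.8% and 7.1% at ρ = 0, 0.5, 0.7, 0.8 and 0.9. The normal approximation is adequate at this size.

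**Step 4: Hochberg in the same simulations.** Claim both times if both P < 0.05; otherwise claim one only if its P < 0.025. The chance of any false claim was about 5.0% at ρ = 0 (exact value 5.0%), then 4.8%, 4.6%, 4.4% and 4.2% at 0.5, 0.7, 0.8 and 0.9.

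**Step 5: price in power.** Assume a true effect of 0.8 SD and ρ = 0.7, with 20 per group. The chance of at least one primary claim, unadjusted versus Hochberg, is:

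- effect at both times: about 81% versus 73%
- effect at one time only: about 72% versus 59%

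**The case against.** The strongest reply is that the inflation is conditional. The document speaks of one primary outcome, and the word joining the two times can be read as requiring both, in which case the error rate never exceeds 5%. That reading is possible, and the excess applies only if either time may count. But the conjunction lists measurement times, just as it does for the secondary outcomes, and the only decision rule in the document judges P values singly. The missing rule is a defect under either reading.

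A second reply is that 9.75% needs zero correlation, which is unlikely for two changes in the same infants from one baseline. That is correct: 9.75% is an upper bound, and about 7% to 9% is the realistic range. It is still above 5%.

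Third, the document lists its tests generically. It does not tie the t-test to this endpoint or state sidedness, and it restricts the test to normal data. The figures therefore rest on assumptions, as set out in the working. Two separate tests is nevertheless what the listed methods lead to, since no joint test is named.

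Fourth, with non-randomised groups, allocation bias may matter more than an excess of 2 to 4 percentage points, and a rule written after the study cannot restore pre-specified control. Both points stand. They limit what the fix achieves, but they do not supply the missing rule.

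**Conclusion.** The concern holds. The plan has two unranked primary time points and no rule for turning two P values into one conclusion.

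If either time counts, the false-positive rate is about 7% to 9% at correlations of 0.9 to 0.5, with a ceiling of 9.75% at zero correlation. If both are required, it runs from 0.25% to 4.3% over correlations of 0 to 0.99. These rates assume two-sided tests, normal data and comparable groups. Imbalance from non-random allocation could raise the rate by an unknown amount that no multiplicity rule removes.

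This should be fixed. The excess is moderate, but it falls on the primary claim and decides what the trial may conclude when 12 h and 24 h differ.

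**What to change.** Add one or two sentences to the Statistical analysis section:

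1. Apply Hochberg across the two primary tests: claim both times if both P < 0.05; otherwise claim one only if its P < 0.025.
2. Report both times with confidence intervals and adjusted P values. The larger P is unchanged; the smaller becomes the lesser of twice itself and the larger P.
3. State when the rule was adopted. If the data had been seen by then, label it post hoc.

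Hochberg suits two positively correlated tests and keeps the full claim when both times reach 0.05. Bonferroni, Holm, a both-required rule or one joint test would also close the gap; what is essential is that one rule is stated. Making 24 h the single primary time, with 12 h tested second, is acceptable only if that order can be shown to predate the data.

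**Cost.** No extra patients. A P value between 0.025 and 0.05 at one time only could no longer be claimed as a primary success. Under the assumptions in the working, the chance of at least one claim falls by about 8 percentage points if the effect is present at both times, and by about 12 to 13 if at one time only. A rule added after the data were seen makes the reporting honest but does not give pre-specified error control.
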